6.2.4.2 Secondary Outcomes

Secondary Outcomes: Total Admitted Hospital Days

Total admitted hospital days will be calculated by two methods for the FAS population. First, LOS will be calculated by inpatient only stays and second, LOS will be calculated by inpatient stays including time spent in prolonged observation status (>1 day). The total admitted hospital-days will be assessed using a similar approach described for the primary analysis and will include all hospital stays. Tables will reflect descriptive statistics for total admitted hospital days and depicted graphically overall using box plots. Hypothesis testing will be performed by a two sided (two sample equal-variance) t-test, with a significance level of 0.05, comparing the difference in total time (in days) spent in hospital between the pre- and post-periods. Violations of assumptions for the t-test in the data will be checked for. An appropriate alternative method, such as the Mann-Whitney U test², will be selected if a major violation to an assumption of the t-test is present. Overall differences in descriptive statistics between the pre- and post-periods for total admitted hospital days will be reported.

Secondary Outcomes: Infection-Related Major Surgical Interventions that Required Operating Room Time

Infection-related major surgical interventions that required operating time will be displayed in tables by initial care, follow-up, and overall for the pre-period and post-period for the FAS population. Patient counts and percentages will be reported for no, any, expected, and unexpected surgical interventions. Differences in proportions between the pre- and post-period will be analyzed by a chi-square test or Fisher's exact test, as appropriate, and given with asymptotic 95% CIs.

Secondary Outcomes: Infection-Related Hospitalizations

Infection-related hospitalizations will be displayed in tables by initial care, follow-up, and overall for the pre-period and post-period for the FAS population. Patient counts and percentages will be reported for none, any, 1, 2, and ≥ 3 infection-related hospitalizations. Differences in proportions between the pre- and post-period will be analyzed by a chi-square test or Fisher's exact test, as appropriate, and given with asymptotic 95% CIs.

Secondary Outcomes: Infection-Related Hospitalizations that Resulted in Admission to ICU

Infection-related hospitalizations that resulted in admission to ICU will be displayed in tables by initial care, follow-up, and overall for the pre-period and

post-period for the FAS population. Patient counts and percentages will be reported for none, any, 1, 2, and ≥ 3 infection-related hospitalizations that resulted in admission to ICU. Differences in proportions between the pre- and post-period will be analyzed by a chi-square test or Fisher's exact test, as appropriate, and given with asymptotic 95% CIs.

Secondary Outcomes: All-Cause Hospitalizations in the 30 Days Post-Discharge from the Hospital

All-cause hospitalizations in the 30 days post-discharge from the hospital will be displayed in tables for the pre-period and post-period for the FAS population. Patient counts and percentages will be reported for none, any, 1, 2, and ≥ 3 all-cause hospitalizations in the 30 days post-discharge from the hospital. Differences in proportions between the pre- and post-period will be analyzed by a chi-square test or Fisher's exact test, as appropriate, and given with asymptotic 95% CIs.

Secondary Outcomes: Infection-Related ED Visits

Infection-related ED visits will be displayed in tables by initial care, follow-up, and overall for the pre-period and post-period for the FAS population. Patient counts and percentages will be reported for none, any, 1, 2, and ≥ 3 infection-related ED visits. These categories will be repeated for all, expected, and unexpected ED visits. Differences in proportions between the pre- and post-period will be analyzed by a chi-square test or Fisher's exact test, as appropriate, and given with asymptotic 95% CIs.

Secondary Outcomes: Infection-Related Outpatient Healthcare Visits

Infection-related outpatient healthcare visits will be displayed in tables by initial care, follow-up, and overall for the pre-period and post-period for the FAS population. Patient counts and percentages will be reported for none, any, 1, 2, and ≥ 3 infection-related outpatient healthcare visits. These categories will be repeated for all, expected, and unexpected outpatient healthcare visits. Differences in proportions between the pre- and post-period will be analyzed by a chi-square test or Fisher's exact test, as appropriate, and given with asymptotic 95% CIs.

Secondary Outcomes: Use of PICC Line or Central Line to Administer Antibiotic Therapy

Use of PICC line, central line or no line to administer antibiotic therapy will be displayed in tables by initial care, follow-up, and overall for the pre-period and post-period for the FAS population. Patient counts and percentages will be presented. Differences in proportions between the pre- and post-period will be analyzed by a chi-square test or Fisher's exact test, as appropriate.

Secondary Outcomes: Infection-related Healthcare Visits Due to PICC Line or Central Line Used to Administer Antibiotic Therapy

Infection-related healthcare visits due to PICC line or central line used to administer antibiotic therapy will be displayed in tables by initial care, follow-

up, and overall by the pre-period and post-period for the FAS population. Patient counts and percentages will be reported for none, any, 1, 2, and ≥ 3 infection-related outpatient healthcare visits. These categories will be repeated for all, expected, and unexpected outpatient healthcare visits. Differences in proportions between the pre- and post-period will be analyzed by a chi-square test or Fisher's exact test, as appropriate, and given with asymptotic 95% CIs.

Secondary Outcomes: Response to Treatment at End of Treatment Visit

Response to treatment at end of treatment visit will be a derived variable and further detail for the derivation is given in Appendix B. Response to treatment at end of treatment visit (complete, partial, failure) will be displayed in tables for the pre-period and post-period for the FAS population. Patient counts and percentages will be presented. Differences in proportions between the pre- and post-period will be analyzed by a chi-square test or Fisher's exact test, as appropriate.

Secondary Outcomes: Serious Adverse Events

Serious adverse events will be reported in a table as presented in section 6.2.7. No formal hypothesis testing will take place.

Secondary Outcomes: Patient Satisfaction with Care

Descriptive statistics for the patient satisfaction questionnaire will be reported within a table by the pre-period and post-period for the FAS population. No scoring or formal hypothesis testing will take place. A listing will display the date of visit the assessment occurred, questions answered, and the response to each question for each patient.

Secondary Outcomes: Patient Work and Productivity Loss

Descriptive statistics for the WPAI questionnaire will be reported in a table by the pre-period and post-period for the FAS population. Summaries will describe the distribution of scores derived at day 14. Scores will be calculated and summarized following the WPAI Score Guidelines (see Appendix D). A listing will display the date of visit the assessment occurred, component scores (absenteeism, impairment while working, overall work impairment, activity impairment), questions answered, and the response to each question for each patient.

Secondary Outcomes: Patient HRQoL

Descriptive statistics for the SF-12 will be reported within a table by the pre-period and post-period for the FAS population. Summaries will describe the distribution of scores derived at baseline and day 14, as well as the distribution of changes in scores from baseline. Scores will be calculated and summarized following the SF-12 scoring manual (see Appendix E). A listing will display the date of visit the assessment occurred, component scores (mental health and physical), questions answered, and the response to each question for each patient.

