2.2 Secondary objectives

Estimate the difference in the following outcomes during initial care (the date of enrollment to 10-14 days) and follow-up (30 days after initial care) comparing ABSSSI patients receiving care before implementation of the new critical and after implementation:

- Total admitted hospital days during initial care and follow-up
- Infection-related major surgical interventions that required operating room time during initial care and follow-up (number of expected major surgeries, number of unexpected major surgeries, and total number of major surgeries)
- Infection-related hospitalizations during initial care and follow-up
- Infection-related hospitalizations during initial care and follow-up that resulted in admission to Intensive Care Unit (ICU)
- All cause hospitalizations in the 30 days post discharge from the hospital
- Infection-related ED visits during initial care and follow-up (number of expected, number of unexpected and number of total ED visits during follow-up)
- Infection-related outpatient healthcare visits (e.g., physicians' office visits, ED visits, infusion center visits, home health visits) during initial care and follow-up (number of expected visits, number of unexpected and total number of visits)
- Use of a PICC line or central line to administer antibiotic therapy during initial care and follow-up (number of patients who have a PICC or central line placed)
- Infection-related healthcare visits (e.g., hospitalizations, ED visits, other outpatient visits) due to PICC line or central line used to administer antibiotic therapy during initial care and follow-up (number of expected visits, unexpected visits and number of total visits)
- Response to treatment at end of treatment visit
- Serious adverse events (SAEs) during initial care and follow-up
- Patient satisfaction with care (subject reported)
- Patient work and productivity loss (subject reported)
- Patient Health-related Quality of Life (HRQoL) (subject reported)

3 Study design

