Infection-related healthcare visits (e.g., hospitalizations, ED visits, other outpatient visits) due to PICC line or central line used to administer antibiotic therapy during initial care and follow up	Unexpected visits due to PICC line (i.e. complications)
	Expected visits due to PICC line (i.e. initial placement, monitoring of PICC line)
	All visits due to PICC line (both unexpected and expected visits)
Response to treatment at end of therapy visit	Response to treatment (healthcare provider assessment) comparing response at the 10-14 day visit (end of therapy visit). Response to treatment will be defined

[figure not shown]

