4.3 Secondary Outcomes

Secondary outcomes will be assessed during initial care (the date of enrollment to day 14) and/or follow-up (30 days after initial care), and include:

[figure not shown]
[figure not shown]
Measure	Definition	Period of Assessment
Total admitted hospital days	Total length of stay (LOS) of all hospitalizations during the 44 days of the study (including initial hospitalization)	Initial care and follow-up
Infection-related major surgical interventions that required operating room time	Number of all, unexpected and expected infection-related major surgical interventions that required operating room time	Initial care and follow-up
Infection-related hospitalizations	Number of infection-related hospitalizations	Initial care and follow-up
Infection-related hospitalizations that resulted in admission to ICU	Number of infection-related hospitalizations resulting in admission to the ICU.	Initial care and follow-up
All-cause hospitalizations in the 30 days following discharge from the initial hospitalization	Number of all hospitalizations for patients after initial hospitalization discharge	Overall, including Initial care and follow-up
Infection-related ED visits	Number of all, unexpected and expected infection-related ED visits	Initial care and follow-up

[figure not shown]
Measure	Definition	Period of Assessment
Infection-related outpatient healthcare visits (e.g., physicians' office visits, ED visits, infusion center visits, home health visits)	Number of all, unexpected and expected infection-related outpatient healthcare visits, generated for all patients and repeated by site.	Initial care and follow-up
Use of PICC line or central line to administer antibiotic therapy	Number of PICC line or central line placement for antibiotic therapy	Initial care and follow-up
Infection-related healthcare visits (e.g., hospitalizations, ED visits, other outpatient visits) due to PICC line or central line used to administer antibiotic therapy	Number of all, unexpected and expected infection-related healthcare visits due to PICC line or central line used to administer antibiotic therapy	Initial care and follow-up
Response to treatment at end of therapy visit	Response to treatment will be defined through an assessment of erythema and the absence of fever at 10-14 days and will be categorized as a complete response, partial response, or failure.	Initial care

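### The SAP's counting rule for PICC- and central-line-related visits names outpatient visits only, so as written it leaves line-related hospitalizations out of the outcome defined to include them

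*SAP*

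**What the plan says.** **Definition.** Protocol 2.2 lists the outcome as "Infection-related healthcare visits (e.g., hospitalizations, ED visits, other outpatient visits) due to PICC line or central line", to be reported as expected, unexpected and total visits. Protocol 4.1.2, Table 3 gives it the same scope and breaks it into three rows. The first is "Unexpected visits due to PICC line (i.e. complications"); the others are expected visits, such as placement and monitoring, and all visits. SAP 4.3 labels the measure "Infection-related healthcare visits (e.g., hospitalizations, ED visits, other outpatient visits) due to PICC line or central line used to administer antibiotic therapy" and defines it as "Number of all, unexpected and expected infection-related healthcare visits due to PICC line or central line used to administer antibiotic therapy".

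**Analysis.** The SAP 6.2.4.2 paragraph for this outcome opens in line with the definition: "Infection-related healthcare visits due to PICC line or central line used to administer antibiotic therapy will be displayed in tables by initial care", then follow-up and overall, by period, in the full analysis set. The two sentences that say what is counted come next: "Patient counts and percentages will be reported for none, any, 1, 2, and ≥ 3 infection-related outpatient healthcare visits", and "These categories will be repeated for all, expected, and unexpected outpatient healthcare visits". The chi-square or Fisher's exact comparison and the asymptotic confidence intervals follow from those counts.

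**Neighbouring outcome.** SAP 4.3 has a separate measure, "Infection-related outpatient healthcare visits (e.g., physicians' office visits, ED visits, infusion center visits, home health visits"). Its paragraph in SAP 6.2.4.2 contains the same two counting sentences, word for word.

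**The concern.** A definition and the rule that implements it should name the same events. Here the definition covers inpatient, ED and other outpatient care caused by the line, while the counting rule names outpatient care only and does not mention the line.

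The outcome bears on a claimed advantage of the pathway. Protocol 1.1.4 says dalbavancin can be given through a peripheral line and does not require a PICC or central line. Visits caused by such lines are therefore a cost of usual care that the pathway might avoid. A hospital admission for a line complication is the heaviest use of care within this outcome, and it is the visit type that the counting sentences leave out. A period comparison that omits it would not estimate the quantity stated in the protocol's secondary objectives.

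**Working it through.** The plan gives no figure to reproduce, and the point depends on no alpha, power, effect size or event rate. The check is a comparison of texts.

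**Step 1. Set definition and counting rule side by side.**

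| Feature | Protocol 2.2 and Table 3; SAP 4.3 | Counting sentences, SAP 6.2.4.2 |
|---|---|---|
| Hospitalizations | Named | Outside the category |
| ED visits | Named | Inside (step 2) |
| Other outpatient visits | Named | Inside |
| Due to the line | Part of the definition | Not repeated; only in heading and lead sentence |
| All, expected, unexpected | Required | Present, but for outpatient visits |

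**Step 2. Establish what counts as outpatient.** Protocol 2.2, Protocol Table 3 and SAP 4.3 all give ED visits as an example of an outpatient healthcare visit. The line outcome's own label puts ED visits before other outpatient visits, which again treats them as outpatient. ED visits therefore survive the counting rule and hospitalizations do not: 3 named types − 2 retained = 1 lost.

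**Step 3. Ask whether the wording is house style.** Five other paragraphs in SAP 6.2.4.2 use the same none, any, 1, 2 and 3-or-more categories: infection-related hospitalizations, those with ICU admission, all-cause hospitalizations after discharge, ED visits and outpatient visits. In each, the counting sentence names that paragraph's own event. Only the line paragraph counts the event of another outcome. Text carried over from the outpatient paragraph is the likely explanation.

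**Step 4. Ask whether a narrowing was intended.** SAP 5.0 lists changes from the protocol's analyses: laboratory-derived infection characteristics dropped, and the preferred tests changed for continuous variables and for proportions. It does not limit line-related visits to outpatient care. SAP 4.3 keeps the full scope.

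**Step 5. Look for another place that settles it.**
- Appendix B, as available, has no derivation for line-related visits.
- The infection-related hospitalization outcome is not split by whether the line was the cause.
- Table 8 covers the secondary outcomes, but the shells are a separate document, which SAP 7.0 cites by a draft file name with placeholders for version and date.
- SAP 6.1.8 says the analyses follow the SAP and its shells. The double programming in SAP 6.1.9 would not catch the error if both programmers worked from the same sentence.

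**Step 6. Take the two possible readings.** If the lead sentence governs, the table counts line-related outpatient visits, ED visits included, and omits line-related hospitalizations. If the counting sentences are taken alone, the table also loses the link to the line. Neither reading gives the defined outcome, and hospitalizations are missing under both.

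**The case against.** The strongest reply is that this is a slip of wording in one paragraph. The heading, the lead sentence and SAP 4.3 all name the full outcome, the Table 8 shell may already have the right rows, and a careful programmer would follow the definition. Much of this stands. It is an internal contradiction, and what would actually be programmed cannot be known from the documents. It does not remove the need to reconcile the text, because even the charitable reading keeps the word outpatient and so excludes hospitalizations.

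Four stronger inferences are tempting, and the documents do not support them.

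- *ED visits for line complications are lost too.* They are not, since both documents class ED visits as outpatient healthcare visits.
- *The table would simply repeat the outpatient table and count clinic visits unrelated to any line.* This requires setting aside the heading, the lead sentence and the SAP 4.3 definition. What can fairly be said is that the counting sentences do not repeat the restriction.
- *Line-related admissions would go uncounted in the trial.* Infection-related hospitalizations and all-cause hospitalizations in the 30 days after discharge are tabulated. Adverse events requiring inpatient hospitalization are SAEs (Protocol 5.4) and appear in SAP Table 9. Listing 8 covers hospitalizations and ED visits. The gap is in attribution to the line, not in capture.
- *A specific number of patients would be missed.* Neither document gives a frequency of line placement or of line complications, so any count would rest on invented rates.

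It is also fair to say that SAP 6.2 calls hypothesis testing of secondary outcomes purely exploratory and not adequately powered, so no confirmatory conclusion depends on this paragraph.

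**Conclusion.** The point holds in limited form. The two counting sentences in SAP 6.2.4.2 contradict the outcome's definition in Protocol 2.2, Protocol Table 3 and SAP 4.3. Followed as written, they omit one of the three named visit types, hospitalizations, from the line-related outcome, and they leave the restriction to line-related visits to be inferred from the heading and lead sentence. No other table listed in SAP 7.0 is described as attributing hospitalizations to the line, so the omitted component could not be read from another planned table.

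The consequence is confined to one exploratory secondary outcome; the primary analysis and the sample size do not depend on it. The conclusion assumes that the SAP text, rather than an unseen table shell, determines what is counted. If the Table 8 shell already follows SAP 4.3, what remains is a contradiction between SAP and shell that still needs correcting. A correction is worthwhile because it costs little and restores a protocol-defined outcome.

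**What to change.** In the line-related paragraph of SAP 6.2.4.2, replace the outpatient phrase in both counting sentences with the outcome's own label from SAP 4.3: "Infection-related healthcare visits (e.g., hospitalizations, ED visits, other outpatient visits) due to PICC line or central line used to administer antibiotic therapy". Keep the none, any, 1, 2 and 3-or-more categories, and apply them to all, expected and unexpected visits, as Protocol Table 3 requires. Then check that the Table 8 shell has rows matching this wording and takes its counts only from visits recorded as due to the line. A breakdown by visit type would be an optional addition; neither document asks for one for this outcome.

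The cost is two sentences in the SAP and a check of one table shell. The change asks for no data beyond what the existing definition already needs, namely a record of whether each visit or admission was due to the line.

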6.2.5 Clinical Assessments

Vital signs including temperature (°C), method of collection of temperature, heart rate (beats per minute), respiratory rate (breaths per minute), systolic BP (mmHg), diastolic BP (mmHg), height (cm), weight (kg) and BMI (kg/m²)

will be summarized at baseline and the 48-72 hours after enrollment follow-up visit (post-period only).

Height is collected in both inches (in) and centimeters (cm) and will be reported in centimeters in the analysis. If height is reported in inches then it will be converted as follows:

$$\text{Height (cm)} = \text{reported value (inches)} * 2.54$$

Weight is collected in both pounds (lbs) and kilograms (kg) and will be reported in kilograms in the analysis. If weight is reported in pounds then it will be converted as follows:

$$\text{Weight (kg)} = \text{reported value (lbs)} * 0.4536$$

Temperature is collected in both degrees Celsius and Fahrenheit and will be reported in degrees Celsius in the analysis. If temperature is reported in degrees Fahrenheit then it will be converted as follows:

$$\text{Temperature (°C)} = (\text{reported value (°F)} - 32) / 1.8$$

Clinical assessments will be summarized with descriptive statistics for baseline and the day 10-14 visit by the pre-period and post-period for the FAS population. Values will be summarized in tables and listings, and in listings, reported with the visit date and change from baseline for follow-up values.

